#### **4.3 Diet, Activities, and Other Restrictions**

##### **4.3.1 Concomitant Medication**

Commercially Confidential Information

Occasional use of paracetamol will be allowed up to a maximum of 4 grams per 24 hours where required, but not on a regular basis. If a concomitant medication is needed during the study, this medication must be recorded on the electronic case report form (eCRF), stating its generic name, time of administration, dose, route and duration, as well as the reason for administration.

Commercially Confidential Information

#### **4.3.2 Caffeine**

Consumption of caffeine- or xanthine- containing products (e.g., coffee, tea, cola drinks and chocolate) must be maintained without a change from well-established habit from 48 hours prior to the Baseline/Pre-dose visit until the Day 21 visit.

Commercially Confidential Information

#### **4.3.4 Physical Activities**

From Screening until the EOS examination, the subjects should refrain from excessive physical exercise and strenuous sports activities (endurance sports).

#### **4.3.5 Dietary Aspects**

No restrictions.

#### **4.3.6 Smoking**

No restrictions.

### **4.4 Withdrawal Criteria**

Participation of a subject in this clinical study may be discontinued for any of the following reasons:

- The subject withdraws consent or requests discontinuation from the study for any reason
- Occurrence of any medical condition or circumstance that exposes the subject to substantial risk and/or does not allow the subject to adhere to the requirements of the protocol
- Any SAE, clinically significant AE, severe laboratory abnormality, intercurrent illness, or other medical condition which indicates to the Investigator that continued participation is not in the best interest of the subject
- Pregnancy

Commercially Confidential Information

- Subject failure to comply with protocol requirements or study-related procedures
- Termination of the study by the Sponsor or the regulatory authority

If a subject withdraws prematurely from the study due to the above criteria or any other reason, study staff should make every effort to complete the full panel of assessments scheduled for the Early Termination visit (Day 14). The reason for subject withdrawal must be documented in the eCRF.

Withdrawn subjects may be replaced per the Sponsor's discretion.

### **4.5 Lost to Follow up**

A subject will be considered lost to follow-up if he or she repeatedly fails to return for scheduled visits and is unable to be contacted by the study site.

The following actions must be taken if a subject fails to return to the clinic for a required study visit:

- The site must attempt to contact the subject and reschedule the missed visit as soon as possible and counsel the subject on the importance of maintaining the assigned visit schedule and ascertain whether or not the subject wishes to and/or should continue in the study.
- Before a subject is deemed lost to follow up, the Investigator or designee must make every effort to regain contact with the subject (where possible, 3 telephone calls and, if

necessary, a certified letter to the subject's last known mailing address or local equivalent methods). These contact attempts should be documented in the subject's medical record.

- Should the subject continue to be unreachable, he/she will be considered to have withdrawn from the study.

## **5 STUDY TREATMENTS**

### **5.1 Treatment Groups**

There will be 1 treatment group.

### **5.2 Rationale for Dosing**

The dose level of CAD-1883 is 300 mg (3 capsules of 100 mg each) twice daily, with the first dose for Day 1 taken in clinic, and the second daily dose taken 4 to 5 hours later on clinic visit Days 1, 7 and 14 only. The second daily dose for all other (at home) days will be taken 8 hours later ( $\pm 2$  hours).

Commercially Confidential Information

### **5.3 Randomization and Blinding**

This will be an open label study with no blinding.

### **5.4 Breaking the Blind**

Not applicable.

### **5.5 Drug Supplies**

#### **5.5.1 Formulation and Packaging**

Cadent Therapeutics, Inc. will provide CAD-1883 as capsules (Coni-Snap Gelatin, Size 4, Swedish Orange) of 100 mg dosage strength in 60-cc wide-mouth round white HDPE unit bottles with 33-mm SecuRx® Closures. Additional information on formulation and packaging can be found in the Pharmacy Manual. A detailed description of the chemistry, manufacturing, and quality controls of CAD-1883 100 mg capsules is provided in the Investigator's Brochure (IB).

#### **5.5.2 Study Drug Preparation and Dispensing**

All study drugs will be dispensed by the Investigator or a person under the Investigator's supervision.

#### **5.5.3 Study Drug Administration**

CAD-1883 is administered orally at the dose of 300 mg (3 capsules of 100 mg each) twice daily, with the first dose for Day 1 taken in clinic, and the second daily dose to be taken 4 to 5 hours later on clinic visit Days 1, 7 and 14 only. The second daily dose for all other (at home) days will be taken 8 hours later ( $\pm 2$  hours). Each subject is provided with a medication diary to denote the date and time of at-home study drug dosing. Dosing instructions for medication intake are provided in the pharmacy manual.

#### **5.5.4 Treatment Compliance**

The subject must return the bottle containing unused capsules (if any) to the study site for a compliance check at the visits specified in the SOA ([Appendix A, Table 2](#)).

### **5.5.5 Storage and Accountability**

The subject kits will be stored at controlled room temperature between +15°C and +25°C in each study site pharmacy, which will be locked with restricted access. No additional procedures are required for the safe handling of the capsules.

Recommendations for subjects: the capsules should be kept in the original packaging (bottles). The bottles should be stored in the subject's home at room temperature and out of reach of children and away from direct sunlight. The study drug must not be given to other persons.

## 6 STUDY PROCEDURES

- Study procedures and their timing are summarized in the SOA ([Appendix A, Table 2](#)). Protocol waivers or exemptions are not allowed.
- Immediate safety concerns should be discussed with the Investigator, Medical Monitor, and Sponsor immediately upon occurrence or awareness to determine if the subject should continue or discontinue study intervention.
- Adherence to the study design requirements, including those specified in the SOA ([Appendix A, Table 2](#)), is essential and required for study conduct.
- All screening evaluations must be completed and reviewed to confirm that potential subjects meet all eligibility criteria. The Investigator will maintain a screening log to record details of all subjects screened and to confirm eligibility or record reasons for screening failure, as applicable. See [Section 6.1.1](#) for information about re-screening subjects.

### 6.1 Study Visits

The study period consists of Screening, Baseline/Pre-dose visit, treatment period, and Follow-up visit for a total study period that could be up to 56 days. Subjects will undergo a screening period of a minimum of 14 days up to a maximum of 35 days, a 1-day Baseline/Pre-dose visit, a Day 1 visit that may occur up to 3 business days post the Baseline/Pre-dose visit, a treatment period for 14 days (including Day 1), and a Follow-up visit at Day 21. All procedures and assessments will occur as indicated in the SOA ([Appendix A, Table 2](#)).

#### 6.1.1 Screening Period

Subjects will undergo a screening period of a minimum of 14 days up to a maximum of 35 days in which the subject will “wash-out” from prior tremorgenic and anti-tremor medications, to allow the effects of previous medication(s) on tremor to be eliminated. During the Screening period, each subject will undergo full assessment including medical and treatment history for ET, physical and neurological examination (including a focused neurological exam to include full assessment of tremor per Movement Disorder Society classification criteria ([Bhatia, 2018](#))), in addition to laboratory testing, 12-lead ECG and other screening assessments as indicated in the SOA ([Appendix A, Table 2](#)). The diagnosis of ET must be established by the Principal Investigator at Screening based on the MDS criteria ([Bhatia, 2018](#)) with a documented severity of tremor based on the clinician-administered TETRAS-PS ([Elble, 2012](#)).

Commercially Confidential Information

Per the Investigator’s discretion, re-testing of any laboratory abnormality at the central lab or at a local lab is permissible, with prior approval from the Medical Monitor.

Subjects who previously failed screening can be invited to re-screen up to two additional times, with recommendation by the Investigator and with approval by the Sponsor.

### **6.1.2 Pre-dose (Baseline) Visit**

At the Baseline/Pre-dose visit, subjects will undergo all required procedures as indicated in the SOA ([Appendix A, Table 2](#)) including confirmation that all eligibility criteria are met. Analysis of the pre-dose laboratory assessments (chemistry, hematology, urinalysis) should be conducted by the Central Laboratory, with the results available and reviewed by the Principal Investigator, or designee, prior to dosing the subject with CAD-1883 (Day 1 visit).

Under exceptional circumstances, the pre-dose laboratory assessments (chemistry, hematology, urinalysis) can be sent for expedited analysis at the local laboratory, along with duplicate samples sent to the Central Laboratory. The results of the above-referenced laboratory assessments should be available and reviewed by the Principal Investigator, or designee, prior to dosing the subject.

Additionally, a urine sample will be collected for determination of baseline levels of composite biomarker panel for renal tubular injury, which is not part of eligibility determination.

### **6.1.3 Day 1 Visit (First In-Clinic Dosing)**

The Day 1 visit may occur up to 3 business days following the Baseline/Pre-dose visit. Baseline/Pre-dose laboratory assessments should be available and reviewed by Principal Investigator, or designee prior to dosing the subject with CAD-1883.

On Day 1, subjects will be dosed in the clinic with the first dose of CAD-1883 300 mg (3 capsules of 100 mg each) and will be monitored in the clinic prior to ingesting the second dose of CAD-1883 300 mg (3 capsules of 100 mg each), 4 to 5 hours later. Additional safety and all efficacy assessments will be completed after the second in clinic dose on Day 1 as indicated in the SOA ([Appendix A, Table 2](#)).

Subjects will be dispensed study drug for continued twice-daily oral self-administration at home.

### **6.1.4 In-clinic Treatment Period Study Visits**

Subjects will return to the site for further assessments on Day 7 (-1 day) and Day 14 ( $\pm 1$  day) and a Follow-up visit (Day 21 [ $\pm 1$  day]). On Days 7 and 14, subjects are instructed to ingest the first daily dose of CAD-1883 of 300 mg (3 capsules of 100 mg each) at home 4 to 5 hours prior to the scheduled and/or anticipated dosing of the second daily dose of CAD-1883 in the clinic. The second daily dose of CAD-1883 300 mg (3 capsules of 100 mg each) will be taken in the clinic, under the supervision of study staff, 4 to 5 hours after the first daily dose, as indicated in the SOA ([Appendix A, Table 2](#)).

### **6.1.5 Intervals Between Site Visits**

Subjects will self-administer CAD-1883 300 mg (3 capsules of 100 mg each) twice-daily. Subjects are instructed to ingest the first daily dose of CAD-1883 at home. The second daily dose will be taken 8 hours ( $\pm 2$  hours) after the first daily dose. Each subject is provided with a medication diary to denote the date and time of at-home study drug dosing, as indicated in the SOA ([Appendix A, Table 2](#)).

Commercially Confidential Information

### **6.1.6 Follow-up Visit**

Upon completion of the 14-day treatment period, subjects will return to the site for the Day 21 Follow-up visit, approximately 7 days ( $\pm 1$  day) after the last dose of study drug was administered. Subjects will complete all study assessments and procedures as indicated in the SOA ([Appendix A, Table 2](#)).

### **6.2 Early Termination Visit and Withdrawal Procedures**

The end of treatment for subjects completing the study is Follow-up Visit on Day 21 ( $\pm 1$  day). For subjects who are withdrawn from the study prior to completion, all Day 14 procedures will be performed at an Early Termination visit as indicated in the SOA ([Appendix A, Table 2](#)) and they will also complete the C-SSRS. Subjects withdrawing from the study early will not receive study drug on-site at the Early Termination visit.

### **6.3 Informed Consent**

After adequate explanation of the aims, methods, objectives of the study and potential hazards of the study drug, a written informed consent from each individual participating in this study will be obtained.

### **6.4 Study Assessments and Procedures**

All study assessments and procedures will be conducted as indicated in the SOA ([Appendix A, Table 2](#)) and as described in [Section 7](#) for safety assessments, [Section 8](#) for efficacy assessments,

Commercially Confidential Information

## 7 SAFETY ASSESSMENTS

### 7.1 Adverse Events

An AE is defined as any untoward medical occurrence in a clinical investigation subject administered a pharmaceutical product, which does not necessarily have a causal relationship with this treatment. An AE can therefore be any unfavorable and/or unintended sign (including an abnormal laboratory finding), symptom, or disease temporally associated with the use of an investigational medicinal product, whether or not related to the investigational medicinal product. All AEs, including observed or volunteered problems, complaints, or symptoms, are to be recorded on the appropriate eCRF.

AEs, which include clinical laboratory test variables, will be monitored and documented from the time the subject signs the informed consent form (ICF) until Follow-up Day 21. Subjects should be instructed to report any AE that they experience to the Investigator, whether or not they think the event is due to study treatment. Beginning at Screening, the Investigators should make an assessment for AEs at each visit and record the event on the appropriate AE eCRF.

Wherever possible, a specific disease or syndrome rather than individual associated signs and symptoms should be identified by the Investigator and recorded on the eCRF. However, if an observed or reported sign or symptom is not considered a component of a specific disease or syndrome by the Investigator, it should be recorded as a separate AE on the eCRF. Additionally, the condition that led to a medical or surgical procedure (e.g., surgery, endoscopy, tooth extraction, or transfusion) should be recorded as an AE, not the procedure itself.

Any medical condition already present at Screening should be recorded as medical history and not be reported as an AE unless the medical condition or signs or symptoms present at pre-dose change in severity, frequency, or seriousness at any time during the study. In this case, it should be reported as an AE.

Clinically significant abnormal laboratory or other examination (e.g., ECG) findings that are detected during the study or are present at Screening and significantly worsen during the study should be reported as AEs, as described below. The Investigator will exercise his or her medical and scientific judgment in deciding whether an abnormal laboratory finding or other abnormal assessment is clinically significant. Clinically significant abnormal laboratory values occurring during the clinical study will be followed until repeat tests return to normal, stabilize, or are no longer clinically significant. Abnormal test results that are determined to be an error should not be reported as an AE. Laboratory abnormalities or other abnormal clinical findings (e.g., ECG abnormalities) should be reported as an AE if any of the following are applicable:

- If an intervention is required as a result of the abnormality
- If action is required to be taken with the study drug as a result of the abnormality
- Based on the clinical judgment of the Investigator

### **7.1.1 Assessment of Adverse Events by the Investigator**

The Investigator will assess the severity (intensity) of each AE as mild, moderate, or severe, and will also categorize each AE as to its potential relationship to study drug using the categories of 'yes' or 'no'.

#### Assessment of severity:

Mild – An event that is easily tolerated and generally not interfering with normal daily activities.

Moderate – An event that is sufficiently discomforting to interfere with normal daily activities.

Severe – An event that is incapacitating with inability to work or perform normal daily activities.

#### Causality assessment:

The relationship of an AE to the administration of the study drug is to be assessed according to the following definitions:

No (unrelated, not related, unlikely to be related) – The time course between the administration of study drug and the occurrence or worsening of the AE rules out a causal relationship and another cause (concomitant drugs, therapies, complications, etc.) is suspected.

Yes (possibly, probably, or definitely related) – The time course between the administration of study drug and the occurrence or worsening of the AE is consistent with a causal relationship and no other cause (concomitant drugs, therapies, complications, etc.) can be identified.

The definition implies a reasonable possibility of a causal relationship between the event and the study drug. This means that there are facts (evidence) or arguments to suggest a causal relationship.

The following factors should also be considered:

- The temporal sequence from study drug administration-

The event should occur after the study drug is given. The length of time from study drug exposure to event should be evaluated in the clinical context of the event.

- Underlying, concomitant, intercurrent diseases-

Each report should be evaluated in the context of the natural history and course of the disease being treated and any other disease the subject may have.

- Concomitant drug-

The other drugs the subject is taking or the treatment the subject receives should be examined to determine whether any of them might be recognized to cause the event in question.

- Known response pattern for this class of study drug-

Clinical and/or preclinical data may indicate whether a particular response is likely to be a class effect.

- Exposure to physical and/or mental stresses-

The exposure to stress might induce adverse changes in the recipient and provide a logical and better explanation for the event.

Commercially Confidential Information

Commercially Confidential Information

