### **9.1. Adverse Events**

Any AE occurring after the date/time of informed consent signature but prior to the first dose of study medication (ie, occurring during the Screening and Baseline periods) will be listed. All AEs that occur after the first dose of study drug will be considered TEAEs. This includes any AEs that started or worsened (if present at baseline, increased in frequency or severity) after taking the first dose of the study drug. For AEs occurring on the date of first dose, if the time of onset is missing, the AE will be assumed to be treatment emergent.

All AEs will be coded using the MedDRA Version 21.1 or higher coding dictionary.

The causal relationship of the AE to the study drug is determined by the investigator as Not Related, Unlikely Related, Possibly Related, Probably Related, and Definitely Related. These will be mapped to Unrelated (*Not Related or Unlikely Related*) and Related (*Possibly Related, Probably Related, and Definitely Related*).

Adverse events severity grades are reported as mild, moderate, or severe.

Summaries of incidence rates (frequencies and percentages) of individual TEAEs will be presented by SOC, PT, and cohort. Such summaries will be displayed for all TEAEs, TEAEs by maximum severity, and TEAEs by relationship.

Each subject will be counted only once within each summation level (SOC and PT). If a subject experiences more than 1 TEAE within each summation level only the TEAE with the strongest relationship or the maximum severity, as appropriate, will be included in the summaries by subject for relationship and severity, respectively. If a particular event is missing the severity and/or relationship, then the strongest possible severity or relationship will be assumed for analysis (severity=severe, relationship = definitely related).

Incidence will be presented by descending frequency of SOC and PT within SOC, and then alphabetically within PT where the incidence is the same.

Missing and partially missing AE start and/or stop dates will be imputed, for the purpose of statistical analysis, according to the specifications described in Section 6.1.9.

Numbers of AEs will also be presented in these AE summary tables.

In the AE data listings, all AEs will be displayed. AEs that are treatment emergent will be flagged.

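### The Yes and No causality definitions in Protocol 7.1.1 cover only two of four combinations of timing and alternative cause, and contradict their own labels

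*Protocol*

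**What the plan says.** Protocol 7.1.1 states that the investigator "will also categorize each AE as to its potential relationship to study drug using the categories of" yes and no. There is no third category.

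The Causality assessment text under 7.1.1 gives each category a label and a two-part definition:

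- The No label reads "No (unrelated, not related, unlikely to be related". Its definition is that the time course "rules out a causal relationship and another cause (concomitant drugs, therapies, complications, etc.) is suspected".
- The Yes label reads "Yes (possibly, probably, or definitely related". Its definition is that the time course "is consistent with a causal relationship and no other cause (concomitant drugs, therapies, complications, etc.) can be identified".

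The next sentence adds: "The definition implies a reasonable possibility of a causal relationship between the event and the study drug". A list of factors to weigh follows: timing, other disease, other drugs, known class effects, and physical or mental stress. The end of this subsection is redacted.

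SAP 9.1 describes a different scale: "The causal relationship of the AE to the study drug is determined by the investigator as Not Related, Unlikely Related, Possibly Related", and upward to probably and definitely related. It maps the two lowest levels to unrelated and the three highest to related. It treats a missing relationship as definitely related. The footnotes to Tables 14.3.1.1 and 14.3.1.4 take related events to be those marked at one of the three highest levels on the case report form.

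**The concern.** A yes/no question needs definitions that between them cover every event. These do not, and the event they miss is a common kind: timing fits the drug, but a concomitant drug or another illness could also explain it. The label and the reasonable-possibility sentence point to Yes, while the Yes definition shuts the event out. Two investigators could code the same event in opposite ways, and each could cite this text.

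The trial has one open-label arm (Protocol 5.1 and 5.3). With no comparator, incidence in the adverse event tables cannot be set against a background rate, so the investigator's judgement is the only attribution they carry. That judgement feeds three places:

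- the related-TEAE and related-SAE rows of SAP Table 14.3.1.1;
- SAP Table 14.3.1.4;
- under Protocol 7.3, whether an SAE arising after the 30-day window is reported at all.

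It may also bear on which events are recognised as suspected reactions for expedited reporting under Protocol 7.5.

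**Working it through.** The plan gives no figure to reproduce, so the check is one of logic and tracing.

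**Step 1: coverage.** Each definition joins two conditions with 'and'. I treat timing as either excluded or consistent, and an alternative cause as either present or absent.

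| Time course | Alternative cause | Meets No? | Meets Yes? | Result |
|---|---|---|---|---|
| Excluded | Present | yes | no | No |
| Excluded | Absent | no | no | neither |
| Consistent | Present | no | no | neither |
| Consistent | Absent | no | yes | Yes |

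Two of 2 × 2 = 4 combinations have a category. The second row does little harm, because an event whose timing excludes the drug would in practice be coded No. The third row is the one that matters.

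The table uses one simplification. No speaks of a cause being suspected, and Yes of a cause being identifiable. If a merely suspected cause does not count as identifiable, some third-row events could still meet Yes. The gap then narrows to identifiable causes, and the text does not say which reading is meant.

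**Step 2: labels against definitions.**

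- The Yes label includes possible and probable relationships. Both ordinarily leave room for another explanation, but the definition allows none that can be identified.
- The No label includes unlikely relationships, which leave some possibility open. The definition requires timing to exclude the drug.
- The reasonable-possibility sentence is a lower bar than the absence of any other cause. The text does not say which governs.
- The list of factors tells the investigator to look for alternatives, but not how to code the event once one is found.

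**Step 3: protocol scale against SAP scale.**

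| Protocol 7.1.1 | Levels named in the protocol label | SAP 9.1 levels mapped to the same group |
|---|---|---|
| No | unrelated, not related, unlikely | not related, unlikely |
| Yes | possible, probable, definite | possible, probable, definite |

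The groupings agree, so the difference between two and five levels changes no count by itself. It does leave open which scale the investigator sees. If the CRF offers a possible level, a third-row event has an obvious place. If it offers only yes and no, it does not.

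**Step 4: what depends on relationship.**

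| Item | Uses relationship? |
|---|---|
| Primary endpoint (Protocol 3.3.1) | no |
| TEAEs by SOC and PT, and by maximum severity (Tables 14.3.1.2, 14.3.1.3) | no |
| SAE reports up to 30 days after the last dose (Protocol 7.3) | no |
| Related rows of Table 14.3.1.1; Table 14.3.1.4 | yes |
| SAE reports after the 30-day window (Protocol 7.3) | yes |
| Expedited reporting (Protocol 7.5) | possibly; the section does not say the investigator's answer alone decides |

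The SAP rule for a missing relationship gives no protection. A third-row event coded No is not missing.

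**The case against.** The best defence is that the surrounding text supplies the missing rule. The reasonable-possibility sentence and the list of factors ask for weighing, not for automatic exclusion. Together with the word possibly in the label, they give an investigator good grounds to answer Yes for a third-row event. SAP 9.1 points the same way if the CRF carries the five levels. The redacted text might also hold further guidance.

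Much of this stands. It shows that a sensible investigator can reach Yes. It does not show that every investigator will, because the Yes definition itself says otherwise, and redacted guidance would not alter the visible wording.

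A reader might infer more: that the wording pushes events out of the related counts, so that drug-related harm is systematically understated. The documents do not support that. The third-row event also fails No, which requires timing to exclude the drug, so nothing in the text forces a No. Undercounting is possible, not certain.

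A reader might also point to the wash-out of earlier tremor medication as a ready alternative cause for early events. Wash-out falls in the screening period, and events that start before the first dose are not TEAEs unless they worsen (SAP 9.1). The visible text does not say how many subjects take such medication.

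**Conclusion.** The defect holds as a fault of wording. The definitions are not exhaustive, and they conflict with their own labels and with the standard stated straight after them. The consequence is inconsistent classification of events with consistent timing and another possible cause. Some may be missing from the related rows of Table 14.3.1.1, from Table 14.3.1.4 and from SAE reporting after 30 days.

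Neither direction nor size can be determined. The documents give no event rates and no share of events with an alternative cause, and any percentage would only return the assumption put into it.

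The importance is low. The primary endpoint, the overall TEAE tables and SAE reporting within 30 days are unaffected. The mismatch between protocol and SAP scales is worth correcting but moves no count alone.

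The conclusion rests on the visible text and on reading each definition's two conditions as both required.

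**What to change.** 1. Reword the two definitions in Protocol 7.1.1 so that every event falls into exactly one. Align them with the protocol's own labels and its reasonable-possibility standard: an identifiable alternative cause should not by itself rule out Yes, and No should also accommodate events judged unlikely to be related.
2. State explicitly how to code consistent timing with another possible cause.
3. Use one relationship scale in Protocol 7.1.1, the CRF and SAP 9.1. If five levels are kept, define each and retain the SAP's mapping to two groups.

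The cost is an edit to protocol text, with matching SAP and CRF wording and a short note to investigators. Sample size, visits, treatment and the planned tables do not change.
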